15.8 MISSING DATE INFORMATION FOR PRIOR OR CONCOMITANT MEDICATIONS

For prior or concomitant medications, including rescue medications, incomplete (ie, partly missing) start dates and/or stop dates will be imputed. When the start date and the stop date are both incomplete for a participant, the start date will be imputed first.

15.8.1 Incomplete Start Date

The following rules will be applied to impute the missing numeric fields for an incomplete prior or concomitant medication start date. If the stop date is complete (or imputed) and the imputed start date is after the stop date, the start date will be imputed using the stop date.

Missing month and day

- If the year of the incomplete start date is the same as the year of the dose of study treatment, the month and day of the dose of study treatment will be assigned to the missing fields

- If the year of the incomplete start date is before the year of the dose of study treatment, *December 31* will be assigned to the missing fields
- If the year of the incomplete start date is after the year of the dose of study treatment, *January 1* will be assigned to the missing fields

Missing month only

- If only the month is missing, the day will be treated as missing and both the month and the day will be replaced according to the above procedure

Missing day only

- If the month and year of the incomplete start date are the same as the month and year of the dose of study treatment, the day of the dose of study treatment will be assigned to the missing day
- If either the year of the incomplete start date is before the year of the date of the dose of study treatment or if both years are the same but the month of the incomplete start date is before the month of the date of the dose of study treatment, the last day of the month will be assigned to the missing day.
- If either the year of the incomplete start date is after the year of the date of the dose of study treatment or if both years are the same but the month of the incomplete start date is after the month of the date of the dose of study treatment, the first day of the month will be assigned to the missing day

15.8.2 Incomplete Stop Date

The following rules will be applied to impute the missing numeric fields for an incomplete prior or concomitant medication stop date. If the date of the study exit is missing, impute it as last visit date recorded. If the imputed stop date is before the start date (imputed or nonimputed start date), the imputed stop date will be equal to the start date.

Missing month and day

- If the year of the incomplete stop date is the same as the year of the study exit, the month and day of the last dose of study treatment will be assigned to the missing fields
- If the year of the incomplete stop date is before the year of the study exit, *December 31* will be assigned to the missing fields
- If the year of the incomplete stop date is after the year of the study exit, *January 1* will be assigned to the missing fields

Missing month only

- If only the month is missing, the day will be treated as missing and both the month and the day will be replaced according to the above procedure

Missing day only

- If the month and year of the incomplete stop date are the same as the month and year of the study exit, the day of the study exit will be assigned to the missing day
- If either the year of the incomplete stop date is before the year of the date of the study exit or if both years are the same but the month of the incomplete stop date is before the month of the date of the study exit, the last day of the month will be assigned to the missing day
- If either the year of the incomplete stop date is after the year of the date of the study exit or if both years are the same but the month of the incomplete stop date is after the month of the date of the study exit, the first day of the month will be assigned to the missing day

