### **7.7.1. Prohibited Treatments and Washout Before the Study**

Prohibited medication washout of pharmacologic therapy to treat symptoms of OAB, including nocturia, must be complete prior to the first screening procedure.

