8.0 DEMOGRAPHICS AND OTHER BASELINE CHARACTERISTICS

All continuous variables will be summarized by number of participants and mean, SD, first quartile, median, minimum, third quartile, and maximum values. Categorical variables will be summarized by number and percentage of participants. All summaries will be performed on the ITT population.

Demographic parameters (age; age group; race; ethnicity; sex), baseline characteristics (weight; height; and body mass index, calculated as weight [kg]/(height [m])²) will be summarized descriptively by treatment group.

The following baseline disease characteristics will be summarized descriptively by treatment group and overall (i.e. pooled across all treatment groups): duration of OAB (in years), average number of UIE, UUIE, UUE, micturition episodes & nocturia episodes per day, volume voided per micturition and PVR urine volume.

Medical history data will be coded using the Medical Dictionary for Regulatory Activities (MedDRA). The number and percentage of participants with medical history ongoing at screening will be summarized by system organ class, preferred term and treatment group. Data for medical history that is not ongoing at screening will be summarized and presented in a similar manner. An overall total will be provided for the study as well as by treatment group.

Prior medication is defined as any medication taken before the date of the first dose of study treatment. Concomitant medication is defined as any medication taken on or after the date of the first dose of study treatment.

Both prior and concomitant medications will be coded using the Anatomical-Therapeutic-Chemical classification text from World Health Organization (WHO) Drug Dictionary. The use of prior and concomitant medications will be summarized by the number and percentage of participants in each treatment group and overall.

Previous pharmacotherapy for OAB are medications that were taken before the first study drug (BOTOX or placebo + Hydrogel admixture) instillation. Information on these is captured in the correspondingly named CRF. The profile of previous OAB pharmacotherapy use will be evaluated in several ways as described below:

- The number and percent of participants who had taken each type of previous OAB pharmacotherapy medication will be presented by WHO DDE base preferred name for each treatment group and overall.

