15.7 MISSING DATE INFORMATION FOR ADVERSE EVENTS

The following imputation rules only apply to cases in which the start date for AEs is incomplete (ie, partly missing).

Missing month and day

- If the year of the incomplete start date is the same as the year of the dose of study treatment, the month and day of the dose of study treatment will be assigned to the missing fields
- If the year of the incomplete start date is before the year of the dose of study treatment, *December 31* will be assigned to the missing fields
- If the year of the incomplete start date is after the year of the dose of study treatment, *January 1* will be assigned to the missing fields

Missing month only

- If only the month is missing, the day will be treated as missing and both the month and the day will be replaced according to the above procedure

Missing day only

- If the month and year of the incomplete start date are the same as the month and year of the dose of study treatment, the day of the dose of study treatment will be assigned to the missing day
- If either the year of the incomplete start date is before the year of the date of the dose of study treatment or if both years are the same but the month of the incomplete start date is before the month of the date of the dose of study treatment, the last day of the month will be assigned to the missing day
- If either the year of the incomplete start date is after the year of the date of the dose of study treatment or if both years are the same but the month of the incomplete start date is after the month of the date of the dose of study treatment, the first day of the month will be assigned to the missing day

If the stop date is complete and the imputed start date as above is after the stop date, the start date will be imputed by the stop date.

If the start date is completely missing and the stop date is complete, the following algorithm will be used to impute the start date:

- If the stop date is after the date of the dose of study treatment, the date of the dose of study treatment will be assigned to the missing start date
- If the stop date is before the date of the dose of study treatment, the stop date will be assigned to the missing start date

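### When both dates of a medication are partial, SAP 15.8.1 and 15.8.2 move opposite dates, and the stated order can tabulate a drug stopped before dosing as concomitant

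*SAP*

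**What the plan says.** All references are to the Stage 2 SAP unless stated.

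- **15.8, order:** "When the start date and the stop date are both incomplete for a participant, the start date will be imputed first".
- **15.8.1, start with only the year known, equal to the dosing year:** "the month and day of the dose of study treatment will be assigned to the missing fields".
- **15.8.1, tie-break:** "If the stop date is complete (or imputed) and the imputed start date is after the stop date, the start date will be imputed using"; in other words, it moves to the stop.
- **15.8.2, stop with only the day missing, in a month before study exit:** the last day of the recorded month is used.
- **15.8.2, tie-break:** when an "imputed stop date is before the start date (imputed or nonimputed start date), the imputed stop date will be equal to the start date".
- **8.0, classification:** "Concomitant medication is defined as any medication taken on or after the date of the first dose of study treatment". Prior medication is anything taken before that date.
- **15.7, adverse events:** "If the stop date is complete and the imputed start date as above is after the stop date, the start date will be" set to the stop date. There is no cap for a stop date that is itself partial.

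The Stage 1 SAP (15.7 to 15.8.2) has the same pair of tie-breaks and the same adverse event rule. Its stop-date rules refer to the last dose of study treatment instead of study exit.

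**The concern.** If both dates are imputed and the stop lands before the start, the conditions of both tie-breaks are met. One moves the start back and the other moves the stop forward, and no sentence ranks them. The order in 15.8 settles it only by implication. When the start is imputed, no imputed stop exists yet, so the 15.8.1 reference to an imputed stop cannot act. The 15.8.2 rule then overwrites the stop.

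This overwriting discards recorded information. The stop month is known and was first imputed correctly within that month, and it is then replaced by a date that the record rules out. The drug changes class, from prior only to concomitant only. Two programmers who each follow one of the two sentences would produce different tables from the same record.

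**Working it through.** The plan gives no figure for this point, so the check applies the rules literally to partial dates. The dosing dates are illustrative assumptions. Study exit is taken at the scheduled Week 24 visit, Day 169 (Stage 2 SAP 15.1), which is dosing date + 168 days.

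**1. One record.** Dosing 10 Jun 2019, exit 25 Nov 2019. Recorded start: 2019 only. Recorded stop: Mar 2019.

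- Start (15.8.1): same year as dosing, so 10 Jun 2019.
- Stop (15.8.2): month before exit, so 31 Mar 2019.
- The stop is before the start, so both tie-breaks apply.

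| Tie-break | Start | Stop | Class under 8.0 |
|---|---|---|---|
| 15.8.1 (start moves) | 31 Mar 2019 | 31 Mar 2019 | prior only |
| 15.8.2 (stop moves; stated order) | 10 Jun 2019 | 10 Jun 2019 | concomitant only |

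Under 15.8.2 the stop lies 30 + 31 + 10 = 71 days after the last day that the record allows.

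**2. All dosing dates in 2019 with this pattern** (start recorded as 2019, stop in an earlier month of 2019). The number of combinations is the sum over dosing months of (days in month) × (month number − 1):

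28×1 + 31×2 + 30×3 + 31×4 + 30×5 + 31×6 + 31×7 + 30×8 + 31×9 + 30×10 + 31×11 = 2,017.

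All 2,017 are concomitant under 15.8.2 and prior only under 15.8.1. The Stage 1 rules give the same 2,017 conflicts, because a stop month before the dosing month also gets its last day there.

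**3. Where the problem stops.**

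- If the stop date is complete, 15.8.1 alone applies and the drug stays prior.
- If start and stop both lie in an earlier year (start 2018, stop Mar 2018), the tie-breaks disagree (31 Mar 2018 against 31 Dec 2018), but the drug is prior either way.
- If the stop month is the dosing month, the rules do not conflict.

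**4. The mirror case.** Same participant, recorded start Sep 2019, recorded stop 2019 only. The start becomes 1 Sep 2019. The stop is in the exit year, so 15.8.2 gives it the month and day of dosing, 10 Jun 2019. Here the 15.8.2 tie-break is the sound one: it raises the stop to 1 Sep, which fits both recorded fields. The 15.8.1 tie-break would pull the start to 10 Jun, before its recorded month. Taking 2019 doses with exit in 2019, and start months after the dosing month up to the exit month, all 1,078 combinations conflict in this way.

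Each tie-break is therefore right for one pattern and wrong for the other. I also ran all year-only and month-known pairs from 2018 to 2020 against every 2019 dosing date, for both stages. Conflicts arose only between one year-only date and one month-known date, never between two dates with equal information.

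**5. Adverse events (15.7).** Dosing 10 Jun 2019, event start recorded as 2019, stop as May 2019. The start is set to 10 Jun. The cap needs a complete stop date, so it does not act, and the event is dated as starting after the month in which it is recorded as ended.

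**The case against.** The strongest reply is that this is a wording ambiguity of little consequence. It needs a year-only start in the dosing year together with a stop that lacks only its day, and it feeds tables that count participants. The documents give no frequency, which may be zero. This stands, and it limits the point to a minor one. It does not make the stated result correct for the records it covers.

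A second reply is that the reference to imputed starts in 15.8.2 does necessary work. That also stands (the mirror case above), and it rules out the simple remedy of always capping the start at the stop.

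A reader might infer more, but the documents do not support it:

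- **An apparent washout breach.** Protocol 7.7.1 says that washout of OAB drugs "must be complete prior to the first screening procedure". But SAP 8.0 gives previous OAB pharmacotherapy its own CRF and its own summaries, and no visible text judges washout, or inclusion in those summaries, from dates imputed under 15.8.
- **A prior-therapy duration of zero.** Start and stop coincide under either tie-break, so the conflict does not cause this.
- **A known number of affected participants.** Nothing in the documents supports any rate.
- **A false treatment-emergent event.** SAP 11.1 requires the event to be present after the first dose, and 15.7 imputes no stop date. The result depends on how that phrase is programmed. Events are collected only from consent, and Stage 2 screening lasts at most 42 days even when extended, so such records should be rare.

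**Conclusion.** The point holds as an error in the written rules, and it is minor. When both dates are partial and the imputed stop precedes the imputed start, the two tie-breaks contradict each other. The stated order turns a drug with a year-only start in the dosing year and an earlier recorded stop month into a concomitant drug dated to the dosing day. This follows from the text for every such record, whatever the dosing date.

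The visible effect is confined to the descriptive prior and concomitant medication tables. The primary ANCOVA uses bladder diary averages and none of these dates. Parts of the Stage 2 SAP are blacked out, so the statement about other outputs covers the visible text only. The gap in 15.7 is real but rare, and its effect on treatment-emergent counts is not established.

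**What to change.** In both SAPs, replace the two opposing tie-breaks for the case where both dates are imputed with one rule:

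1. No imputed date may fall outside its recorded month and year.
2. If the imputed stop precedes the imputed start, the date with less recorded information moves. A year-only start is capped at the stop imputed within its recorded month. A year-only stop is raised to the start imputed within its recorded month.

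Keep the 15.8.2 reference to imputed starts for that last case, and keep both tie-breaks as they are when only one date is imputed. In the first example the rule gives 31 Mar 2019 for both dates (prior). In the mirror case it gives 1 Sep 2019 for both. Because no conflict was found between two dates with equal information, the rule always identifies which date to move.

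In 15.7, extend the cap: an imputed adverse event start may not be later than the last possible day of a partial stop date.

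The cost is a few sentences in 15.7 and 15.8 of each SAP and a small change to the date-imputation program. No new data are needed.

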15.9 CHARACTER VALUES OF CLINICAL LABORATORY PARAMETERS

If the reported value of a clinical laboratory parameter cannot be used in a statistical summary table because, for example, a character string is reported for a parameter of the numeric type, a coded value must be appropriately determined for use in the statistical analyses. The actual values, however, as reported in the database will be presented in the data listings.

shows examples of how some possible laboratory results should be coded for the analysis
[Table 15.9-1](#).

[figure not shown]
Table 15.9-1 Examples of Coding Special Character Values for Clinical Laboratory Parameters

Laboratory Test, SI Unit	Possible Laboratory Results	Coded Value for Analysis
CHEMISTRY		
ALT, U/L	< 5	5
AST, U/L	< 5	5
Bilirubin, total, μ mol/L	< 2	2
URINALYSIS		
Glucose, mmol/L	= OR $> 55, \geq 55, > 0$	Positive
	≤ 0 , negative	Negative
pH	$> 8.0, \geq 8.0$	8.0
	≥ 8.5	8.5
Protein	= OR $> 3.0, \geq 3.0, > 0$	Positive
	≤ 0	Negative

ALT = alanine aminotransferase; AST = aspartate aminotransferase; SI = *Le Système International d'Unités* (International System of Units).

[figure not shown]
16.0**CHANGES TO ANALYSES SPECIFIED IN PROTOCOL**

It is stated in [protocol](#) that all ANCOVA models will include both stratification factors (sex and baseline UUIEs per day) as independent variables. However, some of the ANCOVA models include only sex (male, female) due to the high correlation (observed in previous Allergan studies) between baseline UUIEs (≤ 9 or > 9 episodes/day) and some of the dependent variables derived from the bladder diary data.

ALLERGAN

1839-201-021 Statistical Analysis Plan for Stage 2

Date (DD/MMM/YYYY)/Time (PT)	Signed by:	Justification
10-Jan-2020 15:12 GMT-080		Biostatistics Approval
11-Jan-2020 07:23 GMT-080		Biostatistics Approval
13-Jan-2020 12:58 GMT-080		Biostatistics Approval
15-Jan-2020 08:23 GMT-080		Clinical Development Approval
